6 STUDY SETTING

This is a multicentre study. Data collection as described above will be carried out within two large general acute hospitals in England.

These settings are appropriate as they will allow us to explore how care of people with learning disabilities, including people from minority ethnic backgrounds, is carried out in acute general hospitals.

Local site approvals following NHS regulations will be sought to undertake research through the R & D departments of the two hospital sites, including completing a Research Passport, following HRA and REC permissions.

The same activities will be carried out at both sites with four patients recruited at each site.

7 SAMPLE AND RECRUITMENT

7.1 Eligibility Criteria

7.1.1 Inclusion criteria

- · Adults with a learning disability (over the age of 18)
- · Receiving inpatient care in the hospital site during the data collection period

7.1.2 Exclusion criteria

- Children and young people with learning disabilities (under 18 years of age).
- People living with other kinds of cognitive impairment (not learning disability) e.g. head injury
- People not receiving inpatient care in the hospital sites during the recruitment period
- Patients on the end-of-life care pathway at the point of recruitment into the study
- · Patients in intensive care units at the point of recruitment into the study

7.2 Sampling

.

7.2.1 Size of sample

Our decision to recruit eight patients represents a feasible number to recruit and observe over a fourmonth period at both hospitals concurrently for the purposes of this exploratory study. The rationale for our sample size was based on the known populations of people living with learning disabilities in hospital, our discussions with learning disability liaison nurses working in hospital settings, and expert advice received during the NIHR peer review process during the submission of our grant application.

Our discussions with local learning disability liaison nurses have identified that they have an average admission rate of 20 people with a learning disability every month. This reflects the average admission rates identified in the literature (101). Using GP records and national statistics of hospital admissions, a screening study estimated that within an average-sized local health area approximately 5 adults with learning disabilities will be in hospital every day, each staying for an average of 3.7 days, or as long as 7.4 days in some departments, with significantly longer stays in medical and surgical specialties than members of the general population (102), but this was likely to be an underestimate due to low recording of people with learning disabilities on GP records compared to estimated prevalence in the population. People with severe and profound learning disabilities, a key group of interest in this study, are the most likely people with a learning disability to be identified by hospitals (5,22).

Using this data, extrapolated from the study above, even with longer stays of 7.4 days (30 days/7.4 days stay*5 people= 20) we estimate there will be 80 admissions within each hospital site over the 4 month period of data collection – 160 eligible patients in total – allowing for a cautious 5% recruitment rate.

In addition, we will also be recruiting carers and staff supporting and caring for these eight case study patients. We anticipate this will involve 16-24 carers and 64 members of hospital staff, creating a total sample size of 96.

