7.3.1 Sample identification

Two forms of identification of potential case study patient participants will be carried out concurrently during recruitment periods to maximise identification of potential patient participants.

- 1. Every weekday morning during data collection periods (except when active data collection is happening with a case study participant) Learning Disability Liaison Nurses at both hospitals will be asked to identify wards with potential participants (adults with a learning disability who are current inpatients) and wards with a planned admissions of an adult with a learning disability within the same week.
- 2. With the permission of matrons in both hospitals, JH will make weekly visits (except when active data collection is happening with a case study participant) to the nurses in charge of the medical and surgical wards on each site (due to greater lengths of stay and numbers of people with learning disabilities in these specialisms (5)) and any other wards identified by each site as having more people with learning disabilities attending. She will ask the ward leader to screen their records for any patients with a learning disability currently on the ward (rather than directly through access to care records, which only the patient team can access).

In screening for potential participants, Learning Disability Liaison Nurses and Ward Leaders and Nurses in Charge will be asked to identify people with a learning disability using:

- The reasonable adjustments flag (used nationally) (79) and any further information recorded within it about the nature of 'patient impairment' to identify people with a learning disability.
- The 'hospital learning disabilities flag' used within one of our sites
- Anyone whose record identifies a condition associated with a learning disability (if any one of
 the following was documented in their medical notes: (a) a diagnosis of learning disability (b) a
 condition always accompanied by a degree of learning disability (e.g. Down syndrome, Rett
 syndrome) (c) global developmental delay (following method successfully used by (59))
- Someone identified by the Learning Disability Liaison team or any other relevant professional (e.g. GP, member of a Community Learning Disability Team) as having a learning disability

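### Does the 5% recruitment rate in section 7.2.1 leave too little room, given that 5% of the 160 estimated admissions is exactly the 8 cases needed?

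*Protocol*

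**What the plan says.** Section 7.2.1 takes about 5 adults with learning disabilities in hospital on any day, divides a 30-day month by a 7.4-day stay, and arrives at 20 admissions a month. Local liaison nurses report the same figure, an "average admission rate of 20 people with a learning disability every month". From this, "we estimate there will be 80 admissions within each hospital site over the 4 month period of data collection"; the two sites together become "160 eligible patients in total", "allowing for a cautious 5% recruitment rate". The section gives the average stay as 3.7 days, uses 7.4 as the longer case, and says of its source that "this was likely to be an underestimate due to low recording of people with learning disabilities on GP records".

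Section 7.1.2 excludes patients who are in intensive care or on the end-of-life pathway when recruited. Section 7.3.1 sets up two identification routes, each with an exception. The first runs every weekday morning, "except when active data collection is happening with a case study participant) Learning Disability Liaison Nurses at both hospitals will be asked" to name wards with "adults with a learning disability who are current inpatients" or with admissions planned that week. In the second, the researcher will "make weekly visits (except when active data collection is happening with a case study participant". The same section says both hospitals are worked at the same time. Appendix 2 repeats the weekly ward visits without the exception. The target is 8 cases, 4 per hospital.

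**The concern.** Three things look wrong together. First, an estimate of admissions is relabelled as a count of eligible patients. Some of those admitted will be in intensive care or on an end-of-life pathway, and one person can be admitted more than once. Section 1 says that emergency readmission is more likely in people with profound and multiple learning disabilities, a group the study wants to include.

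Second, 5% of 160 is 8 with nothing left over, so a rate described as cautious seems to be the least that will do.

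Third, both identification routes stop during active data collection, a term the protocol does not define. It could mean the observation days or the whole period from consent to discharge, and at one hospital or both. A long pause at both sites would shrink the pool and could miss short-stay patients. At stake is whether 8 cases can be recruited in four months by a single researcher.

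**Working it through.** **Inputs from the protocol.** Census 5 per day; stay 3.7 days (average) or 7.4 days (longer case); 4 months; 2 sites; target 8 (sections 7.2.1 and Study Summary). Observation on three days or shifts a week, about 20 hours per case (section 5).

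**The plan's own figure.**
- Admissions per site-month: 5 × 30 / 7.4 = 20.3 (stated 20).
- Unrounded total: 20.27 × 4 × 2 = 162.2 (stated 20 × 4 × 2 = 160).
- Rate needed: 8 / 160 = 5.0%.

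The figure reproduces.

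**What the 5% leaves.** 160 − 8 = 152 admissions may be lost for any reason. The rate applies to all admissions, so exclusions, refusals and repeat admissions come out of those 152. It is not an uptake among patients who were found eligible and approached.

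**Exclusions.** The protocol gives no share, so these are illustrations. If a fraction e is excluded, the rate needed among the rest is 8 / [160(1 − e)]: 5.6% for e = 10%, 6.3% for 20%, 7.1% for 30%.

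**Pauses.** Assumptions: a 120-day window, exponentially distributed stays of mean L, and patients still on the ward after a pause can be approached, since screening looks for current inpatients. The share of admissions during a pause of fixed length P that is missed is m = 1 − (L/P)(1 − exp(−P/L)). If pause lengths are themselves exponential with mean P, m = P/(P + L). Admissions lost = 160 × (paused days / 120) × m.

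- *Observation days only*, 8 cases × 3 days = 24 days, so 160 × 24/120 = 32 admissions fall in a pause. For single days m = 0.124 (L = 3.7) or 0.065 (L = 7.4), giving 5.1%. For three consecutive days m = 0.315 or 0.178, giving 5.3% or 5.2%.
- *Whole stay, both sites, P = L = 3.7*: 29.6 paused days, 39.5 admissions in pauses, m = 0.368 to 0.5, 14.5 to 19.7 lost, 8/145.5 to 8/140.3 = 5.5% to 5.7%.
- *Whole stay, both sites, P = L = 7.4*: 59.2 paused days, 78.9 admissions in pauses, 29.0 to 39.5 lost, 8/131.0 to 8/120.5 = 6.1% to 6.6%.
- *Whole stay, own site only*: half the loss, 5.2% to 5.7%.
- *Upper bound, every admission in a two-site pause missed (m = 1)*: 8/120.5 = 6.6% (L = 3.7) to 8/81.1 = 9.9% (L = 7.4).

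**The other direction.** With the 3.7-day average stay, the protocol's formula gives 5 × 30 / 3.7 = 40.5 per site-month, 324 in total, and 8/324 = 2.5%. The nurses' 20 a month, read per hospital, supports 160 rather than 324.

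**The case for a change.** The strongest case for a change is that a planning rate should carry a margin, and this one carries none on its own terms. If the true conversion were 5% of 160, the exact binomial chance of at least 8 cases would be 55%. With 4 needed at each hospital it would be 57% per site, or about 33% for both if the sites are independent. Exclusions and pauses push in the same direction. The halving of the pool through the 7.4-day stay cannot be counted fully as hidden margin, because the nurses' figure independently gives 20 a month. Defining the pause and renaming the pool would cost only wording.

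Part of this stands. The pool consists of admissions, the pause is undefined, and Appendix 2 does not repeat the exception.

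The rest does not carry. The 55% holds only if 5% is the expected conversion, and the protocol puts it forward as a deliberately low one. At 7% the chance is 88% and at 10% it is 99%. Break-even is simply how such a rate is obtained: target divided by pool. The pause figures come from a model that the protocol does not contain, and their upper end needs a pause at both hospitals from consent to discharge with no later approach to patients still on the ward. That reading sits badly with concurrent working at both sites, three observation days a week, and the statement in Appendix 2 that the researcher visits as often as needed. Readmission also gives a second opportunity to approach someone, and the intensive-care exclusion applies only at the point of recruitment.

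**Conclusion.** No change to the plan follows. The calculation is correct, and nothing in the protocol shows that converting one admission in twenty is optimistic. The additional uptake implied by the pauses is 0.1 to 0.3 percentage points on the observation-day reading and 0.5 to 1.6 points if both sites pause for each whole stay. The extreme case is 9.9%. These sizes assume 120 days, mean stays and pauses within 3.7 to 7.4 days and, except in the extreme case, later approach to patients still on the ward. Exclusions would add to them by an amount the protocol does not allow one to estimate.

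Calling the admissions eligible is a slip of wording in a feasibility sentence. Section 7.2.1 also rests the number 8 on what one study can observe, on the nurses' experience and on funder review, and section 7.2.2 judges adequacy by the quality of the sample and by saturation. Correcting the label would alter neither the target nor the conduct nor any finding.

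The undefined pause is missing detail that the one researcher who collects all the data can settle sensibly in the field. Keeping liaison nurses reporting through the pauses would be a trade-off: it would take NHS staff time, which section 8.1 aims to limit, to produce reports that the sole researcher often could not follow up on observation days.

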7.2.2 Sampling technique

Sampling in ethnography requires a flexible, pragmatic approach, using a range of variables that may influence the phenomena, and what is known based on the available literature. Probability sampling is not appropriate, instead non-probability sampling will generate analytically - rather than statistically - generalizable findings (103). The number of sites and participants are considered appropriate on the basis of the quality and appropriateness of the sample and when data saturation has been achieved, rather than on the basis of sample size (103).

We will initially use maximum variation sampling (104) to ensure we include people with learning disabilities who are under-represented in work exploring health inequalities, such as the LeDeR reports (75), and are more likely to have a poor experience of health services (17,23). Given the high representation of research with or through carers, we will also approach people with a range of carer support, including people who attend hospital without carers. However, as the study progresses, this approach will be refined to identify a purposive sample, to ensure our sampling reflects the patient population. Thus, sampling will include people with a learning disability who represent a range of factors that may influence care delivery, and where possible, socio-demographic factors:

- Severity of learning disability (mild to profound)
- Primary reason for the admission, including planned and unplanned admissions.
- People from Black, Asian and Minority Ethnic groups with a learning disability.

- · Expected length of stay
- To include people attending hospital with differing levels of support, who have a full-time family
 or professional carer, or no or limited support.

We will use translation services in NHS settings where required.

7.3 Recruitment

Before recruitment begins the researcher will meet with matrons representing different clinical specialty areas in the hospital, to inform them about the study and answer any questions. The researcher will arrange to visit medical and surgical wards and any other wards known to have significantly more admissions among people with learning disabilities. She will provide study information and discuss the study with the ward leader and with ward staff teams where this is possible (e.g. at handover meetings).

7.3.1 Sample identification

Two forms of identification of potential case study patient participants will be carried out concurrently during recruitment periods to maximise identification of potential patient participants.

- 1. Every weekday morning during data collection periods (except when active data collection is happening with a case study participant) Learning Disability Liaison Nurses at both hospitals will be asked to identify wards with potential participants (adults with a learning disability who are current inpatients) and wards with a planned admissions of an adult with a learning disability within the same week.
- 2. With the permission of matrons in both hospitals, JH will make weekly visits (except when active data collection is happening with a case study participant) to the nurses in charge of the medical and surgical wards on each site (due to greater lengths of stay and numbers of people with learning disabilities in these specialisms (5)) and any other wards identified by each site as having more people with learning disabilities attending. She will ask the ward leader to screen their records for any patients with a learning disability currently on the ward (rather than directly through access to care records, which only the patient team can access).

In screening for potential participants, Learning Disability Liaison Nurses and Ward Leaders and Nurses in Charge will be asked to identify people with a learning disability using:

- The reasonable adjustments flag (used nationally) (79) and any further information recorded within it about the nature of 'patient impairment' to identify people with a learning disability.
- The 'hospital learning disabilities flag' used within one of our sites
- Anyone whose record identifies a condition associated with a learning disability (if any one of
 the following was documented in their medical notes: (a) a diagnosis of learning disability (b) a
 condition always accompanied by a degree of learning disability (e.g. Down syndrome, Rett
 syndrome) (c) global developmental delay (following method successfully used by (59))
- Someone identified by the Learning Disability Liaison team or any other relevant professional (e.g. GP, member of a Community Learning Disability Team) as having a learning disability

As the study progresses, learning disability liaison nurses and ward managers will be asked to identify people in line with recruiting a range of people following the sampling criteria described in 7.2.2 (e.g. by ethnicity and by planned or unplanned admissions).

We will work with both hospitals concurrently to maximise recruitment opportunities with the support of staff (including collaborators).

In all cases of patient identification described above, the researcher will only be told which ward to visit for recruitment and will ask the ward manager to screen her current patient list for any adult with a learning disability. No identifying patient details will be shared with her. The researcher will always discuss the study with the ward manager or 'nurse in charge' on the relevant ward and seek initial verbal consent for her to be present on the ward to carry out observations of care should consent be gained from the patient and their carer. If the nurse in charge agrees, she will ask them to gain initial verbal consent from the patient and/or their carer (if supporting) for the researcher to approach the patient to discuss the study. If they provide consent for her to approach to discuss the study, she will discuss the project when a carer involved in their hospital support is present. If they are alone, she will ask if they would like a friend, carer or supporter to be there when she discusses the study and if so, she will return when that person is available.

7.3.2 Consent

People with learning disabilities

In discussion with ward managers, JH will approach eligible patients and their carers following the screening process described above. She will provide accessible information sheets about the study developed with the PPI groups and PPI lead (FL) and available in either EasyRead or Widget, according to preference) and share a link to a video that outlines the information on information sheets (via a private link on YouTube). There will an opportunity for people to ask questions about the study. For patients with learning disabilities who are assessed to lack capacity to consent, we will seek advice from an appropriate consultee in line with the Mental Capacity Act. The personal consultee cannot also participate in the study as a carer. This means if a carer wishes to participate in the study an alternative personal consultee who knows the person well will be consulted instead. For all participants with a learning disability, we will also use Dewing's model of process consent (105), which conceptualises consent as a continuous process with researchers considering whether a study participant is consenting to each decision across the course of the study. In practice, this means that even if someone has already consented to be observed, every time the researcher starts an observation period, she will remind them of the study and provide details of what it involves and check they are still willing to participate.

For people with learning disabilities who are also non-verbal, this will involve asking carer(s) how the person expresses dissent, fear or other negative emotions. Following approaches used within previous ethnographic research with people with profound learning disabilities JH will continually monitor assent, checking her interpretations with the participant's carer. If the participant or potential participant shows dissent to JH's presence, she will cease data collection or not proceed with the recruitment process.

The researcher will seek verbal and written consent from the patient to access and take brief notes from their medical records and for the researcher to attend and take notes during staff meetings about their care. If they lack capacity to make these decisions, advice will be sought from their consultee.

Patients can participate in the research without giving consent for their medical notes to be accessed by the researcher and/or for the researcher to make notes during staff meetings about their care. This will be made clear in discussion and is clear on the information and consent sheets. If consent is given for accessing medical records, or a consultee advises that they can be accessed, brief notes will be taken to outline the treatments and assessments undertaken. These will be used to support the interviews with patients, who may, due to their learning disability, find it difficult to remember the details of their hospital treatment and assessment

At the beginning of each planned data collection session the researcher will check if the person and (if relevant) their carer(s) are happy for her to continue, including a discussion about whether the person feels too unwell to participate in observations or interviews that day or too unwell to continue participating in the study. This will be done in a way appropriate to that person's ability to communicate and understand. If anyone shows signs of not wanting the researcher to carry out the study with them at that time, she will stop collecting data that day. If this happens again the next day, the researcher will withdraw that person from the study completely. If a patient or carer says at any point they don't want to be in the study anymore, or it is their view (or the view of their personal consultee) that the patient does not wish to participate any longer the researcher will withdraw that person from the study completely.

It is possible that existing participants may move onto an End-of-life care pathway or into an Intensive Care Unit. If this happens, we will review their participation with them with the support of their carer or personal consultee if relevant and withdraw them from the study at this point if they wish.

If a participant with a learning disability wishes to withdraw their data from the study, they can do so during the data collection period, but not afterwards. This is made clear on the information sheets and will be discussed with all potential participants.

Carers

If the participant with a learning disability says they are happy for their carer(s) to be included, the researcher will provide the carer(s) with information and consent forms and discuss the study with them too. The carer will be required to give written consent to participate. If the carer does not wish to take part but the patient does, the researcher won't collect any data about them, including during observations of the patient's care if they are present.

Staff

The study focus is on observing the everyday care provided to people with learning disabilities by nursing and HCA staff (and other clinical staff from a range of disciplines and roles when they are involved in the care of our participants with learning disabilities). We have built on the approaches

used in previous NIHR grants using observations, approved by the HRA (NIHR13290; NIHR170503) and agreed this process with guidance from our NHS collaborators.

When consent has been gained for a patient to participate in the study, written consent will be sought from the ward manager or nurse in charge for the researcher to be present on the ward and observe care. The researcher will put up posters about the research in prominent places and leave information sheets at the nurse's station. The researcher will request that the relevant member of staff add a research entry to the patient's medical notes documenting their consent process according to local standard research policy.

The researcher will sit near the patient participant during her observations, explain the study and seek verbal consent from staff. Staff members can cease participation at any point during the study.

Nursing staff will be approached at a time that does not interrupt care to ask for full written consent to participate. Should a staff member decline to give written consent, any data collected about or from them during that observation period will be destroyed and they will not be observed in any subsequent care observations. However as notes on care provided by staff are anonymous, it will not be possible to remove data about prior observations on different shifts.

Written consent from the ward manager will be sought for attending meeting discussions about the patient's care. The researcher will ask for verbal consent from all staff in the meeting and if all staff do not agree, she will not take notes of their contribution. It is not practical to take consent from staff from other parts of the hospital as this may entail interrupting ward processes or interventions. Instead, posters giving information about observations on the ward will be prominently placed at the entrance to the room where observation of the patient is taking place. As described above, a note will be added to the patient's medical record to identify them as a participant in research, according to local standard research procedures. The researcher will carry information sheets and be available to answer questions and will take verbal consent from all staff when it does not interfere with clinical care processes or the work of the ward. An observation will be ceased should any staff member raise any concerns about being observed.

If the patient participant moves to another ward during data collection (including into an Intensive Care Unit or after moving onto an End-of-life care pathway), the researcher will explain the study to the new ward manager and seek initial verbal consent to continue the study on that ward if the patient participant (or on advice from a consultee) wishes to continue. She will check that the patient and their carers (if relevant) are happy to continue with the study on this new ward. She will then use the same recruitment and consent process for the ward manager and staff as described above, for this new ward.

RIGHT TO WITHDRAW

The participant will remain free to withdraw at any time from the study without giving reasons and without prejudicing his/her further treatment and will be provided with a contact point where he/she may obtain further information about the study. Participant withdrawal of consent from the study will be explicitly documented in the source documents.

